Protocol Title: Ultrasound Microbubble Destruction for Improving Radioembolization Therapy of Hepatocellular Carcinoma

Trial Objectives: The primary objective of this trial is to:

· Characterize the ability of localized ultrasound contrast agent destruction to improve hepatocellular carcinoma (HCC) response to Y90 radioembolization.

The secondary aim of this trial is to:

· determine if contrast-enhanced ultrasound estimated tumor perfusion can reliably predict HCC response to radioembolization 1-14 days post treatment.

Trial Design: This is an open-label, randomized trial that will be conducted at one clinical site to determine if ultrasound-triggered microbubble destruction (UTMD) can be used to improve radioembolization of HCC. The subject population will be patients scheduled for radioembolization of a previously untreated HCC mass at Thomas Jefferson University. Patients will be randomly assigned to either the experimental (UTMD + radioembolization) or control group (radioembolization alone) by the research coordinator using a random assignment generator. For patients assigned to the experimental group, the study will consist of up to three contrast-enhanced ultrasound (CEUS) exams 1-6 hours post radioembolization, and approximately 7 and 14 days post treatment. Treatment response will be evaluated using modified response evaluation criteria in solid tumors (mRECIST) at 1 and 3-4 months post treatment based on the patient's clinically scheduled contrast-enhanced MRI or CT. For patients assigned to the control group, only outcomes data will be collected (without intervention).

Ultrasound imaging will be performed using a state of the art commercial ultrasound scanner with a curvilinear transducer. As part of each CEUS exam, patients will first undergo baseline grayscale B-mode and power Doppler imaging (PDI) of the treated mass. Patients will then receive an infusion of the ultrasound contrast agent (UCA) Optison (GE Healthcare, Princeton, NJ), while being imaged with two-dimensional (2D) dual mode B-mode / coded harmonic imaging. Once the presence of contrast has been confirmed in the tumor, a series of flash-replenishment sequences will be generated to destroy UCA within a region of interest encompassing the tumor. This sequence will be repeated at imaging planes throughout the tumor for the duration of the infusion.

Trial Population: This trial will consist of up to 104 adults (52 per group) scheduled for radioembolization of a previously untreated HCC mass less than 6 cm in diameter at Thomas Jefferson University.

Trial Procedures: Subjects eligible for trial enrollment will be identified by Jefferson's patient population of subjects being seen for sub-lobar radioembolization of HCC. These patients will be accrued from the Hepatology department, as well as from the HCC Multidisciplinary Tumor Board of the Kimmel Cancer Center at Thomas Jefferson University. A research coordinator will explain the study to the patient. The patient will be given time to consider the risks and benefits of the study and ask questions about participation. The coordinator will review the consent form with the patient and then the patient will be given the form to review. The patient, coordinator, and a study investigator will all sign the consent form. The patient will be given a copy of the signed consent form for their records. A research coordinator will explain the study to the patient. The patient will be given time to consider the risks and benefits of the study and ask questions about participation before providing informed consent. If the subject is a woman of childbearing potential, she will have a urine pregnancy test (the results of which will be made available to her prior to study initiation) prior to each ultrasound exam. Patients will be randomly assigned to either the experimental (UTMD + radioembolization) or control group (radioembolization alone) by the research coordinator using a random assignment generator.

All patients will undergo single-photon emission computed tomography (SPECT) imaging as part of their standard of care to confirm effective localization of the Y90 beads. For research purposes, imaging of the chest will be performed when possible to assess extrahepatic distribution of Y90 using a planar imaging acquisition. For patients in the experimental group, a brief abdominal ultrasound (without contrast) will also be performed prior to radioembolization to ensure the target lesion is visible on ultrasound. Imaging will be performed an ultrasonographer with experience in liver imaging) using an S3000 or Sequoia scanner with a 6C1, 5C1 or DAX probe and flash-replenishment and a nonlinear imaging package (Siemens Medical Solutions, Mountain View, CA). Ultrasound exams will take place 1-6 hours post radioembolization in Thomas Jefferson University's short procedure recovery unit, and approximately 7, and 14 days post treatment in Thomas Jefferson University's Interventional Radiology Division. Both of these locations have full time nursing support and with patient physiological monitoring. All contrast injections will be supervised by a board certified physician with resuscitation equipment in immediate proximity during contrast-enhanced ultrasound (CEUS) exam. The entire ultrasound imaging protocol will require approximately 90 mins including a 30 min observation period. These time points are based on times when patients are still present or returning to the hospital for regular follow up and when the Y-90 spheres are

still active. Patient vital signs will be monitored and recorded throughout the visit.

CEUS studies will only be conducted with patients assigned to the experimental group (UTMD + radioembolization). Five milliliters of activated Optison will be suspended in 50 ml of saline and infused through an angiocatheter placed in a peripheral arm vein at a rate of 120 ml/hour. This total Optison administration falls within the product insert dosage guidelines (up to 5 ml within a 10 minute period and up to 8.7 ml in any one study). After confirmation of contrast-enhancement within the mass, a series of ultrasound-triggered microbubble destruction (UTMD)-replenishment sequences will be generated to cavitate UCA within the imaging plane. The patient will be asked to temporarily halt respiration while a 4 second UTMD pulse is initiated (approximate transmit parameters of MI = 1.13 at 1.5 MHz, transmitting 2.3 µs pulses at a pulse repetition frequency of 100 Hz), followed by nonlinear imaging of contrast replenishment at lower intensity using Cadence Pulse Sequencing (MI = 0.06) for 10 seconds. Following patient respiration, this sequence will be repeated at multiple imaging planes throughout the tumor and then repeated throughout the entire tumor volume for the duration of the infusion (UTMD expected in 10-20 planes, repeated 3-4 times). In the few patients with multiple Y-90 treated tumors, the largest tumor will be selected for UTMD therapy and outcomes compared to the non-UTMD treated tumors outside the acoustic field.

The primary measure of tumor response will be evaluated using mRECIST criteria as determined by Drs. [name] and [name] in consensus using the patients clinically scheduled 3-4 month contrast enhanced MRI or CT. As a secondary measure of tumor response, changes in alpha fetal protein (AFP; collected as blood samples at approximately one month post embolization as standard of care) will be recorded when clinically available. Tumoral perfusion for each imaging plane will also be calculated as the slope of contrast reperfusion based on change in signal intensity over time. Perfusion values for each plane will then be averaged over the entire mass and normalized to values immediately post treatment (day 1). Finally, each patient's progression free survival and overall survival will be monitored, although this is a tertiary outcome for this study and many patients are expected to surpass the timeline of this pilot study. Safety outcomes will be determined using changes in vital signs, observed and self-reported adverse events, and changes in liver function tests (LFTs) at approximately 1 month post-embolization when available (preformed as part of clinical standard of care). Liver function tests (LFTs) include blood tests for alanine aminotransferase, alkaline phosphatase, asparate aminotransferase, bilirubin, albumin, total protein, and prothrombin time. SPECT imaging will be evaluated for all available cases by two blinded radiologists to evaluate if the initial UTMD session skews Therasphere distribution in the liver.

The proposed agent for the current study, Optison™ is a sterile non-pyrogenic suspension of encapsulated perflutren microbubbles [Goldberg et al 2001; Miller & Nanda 2004]. The contrast agent is consists of a human serum albumin shell with perflutren core and contains 5.0 - 8.0 x 10⁸ microspheres/ ml. The microbubble agent is supplied in a standard-size 3 ml vial and is prepared by manually shaking the vial. Optison will be stored in a secure refrigerator, with only the study investigators and research personnel having access. Optison is currently only approved for use in echocardiography. The agent will be used as an off-label indication for this study, but within approved dosage recommendations.

Statistical Methodology: This project is a pilot study to determine if microbubble destruction and reperfusion can used to improve treatment response of HCC to radioembolization and predict early treatment response.

Our statistical analysis will address two major questions:

- 1. Does the systematic destruction of UCA within HCC masses treated by radioembolization improve treatment response relative to masses treated by radioembolization alone?
- 2. Do CEUS-based tumoral perfusion measurements provide an earlier indicator of radioembolization treatment response in HCC liver masses?

All statistical analysis will be performed by [name] (SKCC Biostatistics Core and faculty member) using SAS version 9.4 (Cary, NC). Aim 1: The primary hypothesis that UTMD improves the effect of radioembolization on tumor response in HCC patients will be tested with a non-parametric Mann-Whitney U-test of the difference in response distributions between control (radioembolization alone) and experimental group (UTMD + radioembolization), measured at 3-4 months post treatment. To test if tumor perfusion measured by CEUS between UTMD pulses predicts HCC response to radioembolization, perfusion will be characterized in terms of contrast replenishment time intensity curves fit with a 2-parameter exponential recovery curve as described above. The relationship between the normalized profusion values from this image processing and the patients' subsequent mRECIST scores in the UTMD + radioembolization group will be evaluated with Spearman's rank order correlation.

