4.1 Inclusion Criteria

All subjects accepted for this trial must:

- Be scheduled for sub-lobar radioembolization therapy of a previously untreated HCC mass < 6 cm visible on grayscale ultrasound.
- Be at least 18 years of age.
- Be medically stable.
- If a female of child-bearing age, have a negative pregnancy test prior to each ultrasound exam.
- Have signed Informed Consent to participate in the study.

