6.5 Efficacy Assessments

The primary measure of tumor response will be evaluated using mRECIST criteria as determined by Drs. [name] and [name] in consensus using the patients clinically scheduled 3-4 month contrast enhanced MRI or CT. As a secondary measure of tumor response, changes in alpha fetal protein (AFP; collected as blood samples at 1 month as standard of care) will be recorded. Finally, each patient's progression free survival and overall survival will be monitored, although this is a tertiary outcome for this study and many patients are expected to surpass the timeline of this pilot study. Safety outcomes will be determined using changes in vital signs, observed and self-reported adverse events, and changes in liver function tests (LFTs) at 1 and month post-embolization (preformed as part of clinical standard of care). Liver function tests

(LFTs) include blood tests for alanine aminotransferase, alkaline phosphatase, asparate aminotransferase, bilirubin, albumin, total protein, and prothrombin time. SPECT imaging will be evaluated for all available cases by two blinded radiologists to evaluate if the initial UTMD session skews Therasphere distribution in the liver.

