7.2.1 Sample Size Calculation

Aim 1: Little is known about the effect of UTMD on radioembolization in humans. When comparing similar groups in our animal studies, we observed relative effect sizes of 0.4 and 0.9 for tumor growth and survival, respectively. These animal study results may not apply directly to humans, but they demonstrate that large effect sizes are plausible for this intervention in subjects with HCC tumors. Under these assumptions, we have determined that a sample size of 52 patients randomized to each group would be needed in order for a Mann-Whitney U-test to have 85% power to detect a similarly moderately large relative effect of UTMD on the mRECIST score (i.e., 0.6) with a 5% type I error rate. A similar analysis is planned to compare mRECIST evaluations between 1 month and 3-4 month MRI to determine if earlier cross-sectional imaging can be used to predict long-term treatment response. Relative effect sizes for LFT, AFP, pathology, blinded reads from SPECT, planar imaging, and time to next treatment are expected to be similarly large and will also be evaluated using appropriate non-parametric or exact tests, and are each subject to the same power considerations as for the primary endpoint. Confounding of the results will be investigated and potential confounders will be included in ordinary least squares (OLS) regression models (or quantile regression models, depending on the adequacy of the data meeting OLS modeling assumptions) of these endpoints. Aim 2: A sample size of 52 would provide a two-sided test having 5% type I error rate at least 80% power to detect a Spearman's correlation of 0.4 or greater in the population. Confounding will also be evaluated for this aim and regression analysis will be considered similarly as described for Aim 1.

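### Section 7.2.1 gives the AFP comparison the primary endpoint's power, but AFP is recorded only where available and no raised baseline is required, so that power is not delivered

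*Combined protocol and SAP*

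**What the plan says.** AFP change is a secondary response measure in three places.

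- Synopsis, Trial Procedures: "As a secondary measure of tumor response, changes in alpha fetal protein (AFP; collected as blood samples at approximately one month post embolization as standard" ... The sentence ends by limiting recording to values that are clinically available.
- Section 3, Trial Design: the same measure, again only when a value is available.
- Section 6.5, without that limit: "As a secondary measure of tumor response, changes in alpha fetal protein (AFP; collected as blood samples at 1 month as standard of care) will" ...

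All three time the follow-up sample at about one month. None defines an AFP response, a change metric (absolute, percent or log) or a set of patients evaluable for AFP.

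The disease criterion in section 4.1 is "Be scheduled for sub-lobar radioembolization therapy of a previously untreated HCC mass < 6 cm visible on grayscale ultrasound". Neither 4.1 nor 4.2 mentions AFP.

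For the primary endpoint, section 7.2.1 states that "a sample size of 52 patients randomized to each group would be needed". The target is given as "Mann-Whitney U-test to have 85% power to detect a similarly moderately large relative effect of UTMD on the mRECIST score (i.e., 0.6"). The type I error rate is 5%. The section then lists AFP among several further endpoints whose effects should be about as large, to be compared by suitable non-parametric or exact tests, and says they "are each subject to the same power considerations as for the primary endpoint". The only effect-size evidence offered is animal tumour growth and survival; there are no AFP data.

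**The concern.** The primary endpoint's power carries over to AFP only if AFP has the same number of analysable patients and the same effect across all of them. The plan secures neither.

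- **Number.** AFP comes from routine care and is recorded if it exists, so fewer than 52 per group may contribute.
- **Effect.** If response is read as a fall in AFP, a patient whose value is not raised before treatment has little or no room to fall, whether or not the tumour responds. Such patients add to the ranking but contribute little or no difference between arms.

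At stake is how a secondary result is read. Against a stated 85% power, a non-significant AFP comparison looks more informative than it would be.

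**Working it through.** **Inputs.** From 7.2.1: 52 per group, effect 0.6 (read as a standardised shift), Mann-Whitney test, 5% type I error, 85% power. Sidedness is not given for Aim 1; two-sided is taken from Aim 2 ("A sample size of 52 would provide a two-sided test having 5% type I error rate"). Assumed, because the documents give no figure: the share of patients with AFP values, the share with normal pre-treatment AFP, and where those patients fall in the ranking.

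**1. The plan's own figure.** The t-test size is 2 × (1.96 + 1.036)² / 0.6² = 49.9, so 50 per arm. Dividing by the Mann-Whitney efficiency 3/π = 0.955 gives 52.4. In reverse, power = Φ(δ√(m/2) − 1.96) with m = 52 × 0.955 = 49.7, which gives Φ(2.990 − 1.96) = 84.8%. The stated 52 and 85% reproduce. A one-sided test would need 42 per arm. Reading 0.6 as a probability of superiority would need 150. The two-sided standardised shift is therefore the reading that fits.

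**2. Missing AFP only** (effect 0.6 in everyone with a value).
- 80% available: n = 41.6, m = 39.7, Φ(2.674 − 1.96) = 76%.
- 50% available: n = 26, m = 24.8, Φ(2.114 − 1.96) = 56%.

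**3. Normal baseline AFP only** (full availability, effect 0.6 in raised-AFP patients, none in the rest). With f the share raised, the simple pooled approximation uses effect 0.6f at 52 per arm. The restricted analysis uses effect 0.6 at 52f per arm. At 20% normal:
- Pooled: effect 0.48, Φ(2.392 − 1.96) = 67%.
- Restricted: n = 41.6, Φ(2.674 − 1.96) = 76%.

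The pooled formula ignores where normal-AFP patients fall in the ranking, so Mann-Whitney tests were also simulated with several placements.

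| Share normal (assumed) | Pooled, formula | Pooled, simulated range | Restricted, formula | Restricted, simulated |
|---|---|---|---|---|
| 10% | 77% | 66-79% | 81% | 80% |
| 20% | 67% | 50-72% | 76% | 75% |
| 30% | 55% | 32-67% | 71% | 69% |
| 50% | 32% | 14-49% | 56% | 54% |

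Placement matters a good deal. With normal-AFP patients close to the control mean (SD 0.2), pooled power is about 77/69/62/40% at these four shares. With them 0.8 SD towards no fall, it is about 73/62/49/25%. Power is lower still if they lie further out.

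Restriction was never worse than pooling in the patterns tried. Its gain ran from about 1 point (80 − 79, at 10% normal) to 40 points (54 − 14, at 50% normal). It did not restore 85% at any share.

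**4. Both together, as an illustration.** With 80% available and 20% of those normal:
- Pooled: m = 39.7, effect 0.48, Φ(2.139 − 1.96) = 57%.
- Restricted: n = 33.3, m = 31.8, effect 0.6, Φ(2.392 − 1.96) = 67%.

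**The case against.** **The plan can be defended on several grounds.** AFP is one of several non-primary measures in a study that calls itself a pilot. The test is left open, and 7.2.1 allows potential confounders into regression models, which could deal with chance imbalance in baseline AFP. The remark about power may mean only that sample size and error rate are shared. The 0.6 could also be meant as the average effect over all patients, with any dilution already included.

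**What stands.** The low rank of the endpoint stands and sets the severity. Regression could absorb some imbalance between arms, but it does not define who can show a response. The milder reading of the power remark is hard to hold, because the same sentence expects AFP effects of similar size: equal effect, number and error rate mean equal power. If 0.6 is an all-patient average, the effect in raised-AFP patients would have to be 0.6/f, or 1.2 at 50% normal. Nothing in the documents supports that, and missing values would still reduce power.

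**Stronger readings a reader might infer, which the documents do not support:**
- That AFP is planned for every patient. The Synopsis and section 3 limit it to available values; only 6.5 omits this.
- That a patient with normal AFP is scored as a non-responder. No AFP response is defined, and lack of room to fall is a reasonable premise from outside the text.
- That power certainly falls far below 85%. At 10% normal the loss may be only about 6 points (85 − 79), though it could reach 19 (85 − 66).
- That a null AFP result would count against the primary finding. The text ranks AFP below mRECIST and does not say this.
- That chance imbalance in the share with normal AFP biases the comparison. Under randomisation it adds noise, not systematic error.

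**Conclusion.** The point holds as a minor one. The power that 7.2.1 lends to AFP is unsupported, because it needs a value from all 52 patients per group and an effect of 0.6 across all of them.

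The loss from missing values follows from the plan's own inputs once an availability is assumed. The loss from normal baselines rests on two further things the documents do not give: the share of such patients, and the premise that their AFP has little room to fall. Its direction was the same in every pattern tried, but its size ranges from modest to severe, so no single figure should be quoted. The primary mRECIST comparison and its sample size are untouched.

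**What to change.** In 6.5 and 7.2.1, state that the main AFP comparison is made in patients with a pre-treatment AFP above the laboratory's upper limit of normal and a 1-month value. Report the result in all patients with values as descriptive. Because a raised pre-treatment AFP is a baseline characteristic, pre-specifying it keeps the randomised comparison within that subset; availability of the 1-month value is a separate matter, so report the number with a value by arm. Carry the availability wording of the Synopsis and section 3 into 6.5, so that the three places agree.

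In 7.2.1, remove AFP from the equal-power sentence, or restate its power for the expected number of evaluable patients.

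The cost is a few sentences, with no new patients or procedures. The downside is a smaller analysed number and a less favourable stated power for one secondary endpoint.

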1. INTRODUCTION

Hepatocellular carcinoma is the third leading cause of cancer mortality worldwide and becoming increasingly common [Alterkruse et al. 2009]. Survival one year after diagnosis is less than 50%, and is worse in patients with advanced disease [Alterkruse et al. 2009]. Because systemic therapies have been proven largely ineffective, embolization represents the current clinical standard for treatment of non-resectable hepatocellular carcinomas [Llovet and Bruix 2003]. Embolization of HCC can be performed via

transarterial chemoembolization or radioembolization. Radioembolization for HCC is performed using TheraSpheres (BTG International). TheraSpheres consist of 20-30 µm glass beads containing yttrium-90 isotopes and the product has been authorized by the FDA with a Humanitarian Device Exemption for the treatment of unresectable hepatocellular carcinoma and our institutional review board has approved these agents for the treatment of HCC. These spheres are locally delivered via a catheter temporarily placed in the hepatic artery that supplies blood flow to the tumor thereby providing a localized and sustained release of radiation. Dosages range from 110-150 Gy. Yttrium-90 undergoes pure beta emission as it decays to stable zirconium-90 with a half-life of 64 hours and average energy emission of 0.94 MeV. The local beta emissions from this technique have been shown to provide therapeutic effect within the tumor [Herba et al. 1988; Houle et al. 1989]. Treatment response is then monitored using contrast-enhanced MRI or CT at 1 month and 3-4 months post treatment response.

Ultrasound contrast agents are gas filled microbubbles, encapsulated by a lipid shell for stability. These agents are small enough (1-8 µm in diameter), to pass through the pulmonary capillaries, but are still restricted to the vascular system [Goldberg et al. 2001]. These microbubbles have been approved for use in echocardiography in the United States and also for the characterization of liver lesions throughout Europe and Asia [Bouakaz and de Jong, 2007]. Our group has demonstrated the exceptional safety and accuracy of CEUS for monitoring chemoembolization of HCC [[name] et al. 2015], and have also observed that UCA perfuse into HCC post radioembolization in these patients. These UCA can also be destroyed in the liver using commercially available flash-replenishment packages which enable visualization and quantification of contrast perfusion [Wakui et al. 2011; Shiraishi et al. 2008; Lefort T, et al. 2012]. These flashreplenishment sequences are performed using commercially available packages that generate a higher intensity (but still well within FDA MI limits) pulse within a selected region of interest to generate UCA cavitation, followed by lower MI nonlinear imaging to visualize contrast reperfusion. Microbubble cavitation has been demonstrated to temporarily increase both cellular and vascular permeability, making it a potential tool for improving localized chemotherapy [Kotopoulis et al. 2013]. Importantly, localized microbubble cavitation has also recently been shown to sensitize tissue to radiotherapy by inducing vascular endothelial cell apoptosis [Kim et al. 2014; Al-Mahrouki et al. 2014; Tran et al. 2012; Czarnota et. al 2012]. Thus, localized destruction of UCA after radioembolization of HCC may potentially improve tumor response by selectively sensitizing malignant tissue to radiotherapy. In this study, we propose a pilot clinical trial using localized UCA cavitation/reperfusion imaging to both improve patient outcomes and predict treatment response earlier than the current clinical standards.

